melatonin. Melatonin for difficulties with sleep onset is permissible and is not included in the count of psychotropic medications.

- b. The use of anti-epileptics for other indications such as the treatment of mood disorders counts towards the limit of permitted psychotropic medications.
- c. Anti-epileptic medications used for treatment of seizures does not count towards the limit of psychotropic medications.
- 30. Current treatment with insulin or treatment within the last 12 weeks prior to commencement of IMP.
- 31. Current treatment with IGF-1 or treatment within 6 months of commencement of the IMP.
- 32. Current treatment with growth hormone or treatment within 12 months of commencement of the IMP.
- 33. Non-pharmacologic somatic treatment (e.g., a ketogenic diet or vagal nerve stimulation) whose dosing regimen has not been stable at least 4 weeks prior to the start of Screening. If the treatment was discontinued, the discontinuation must have occurred no fewer than 2 weeks before the start of Screening.
- 34. Patients planning to start a new behavioral, educational, or cognitive therapy during the period of the study or those who have begun a new behavioral or cognitive therapy regimen within 4 weeks prior to the start of Screening.
 - a. Note: changes to an ongoing treatment regimen that are due to school schedules or are otherwise seasonally related are not exclusionary as long as they are consistent with their typical type and pattern of behavioral treatment.
- 35. Seizure medication whose dosing regimen is not stable 8 weeks prior to commencing IMP. Adjustments for changes in weight or age are allowable. If the treatment was discontinued, the discontinuation must have occurred no fewer than 2 weeks before the start of Screening.
- 36. Psychotropic medications or any other medication used for a chronic illness (not including antibiotics, pain relievers, anti-diarrheals, and laxatives) whose doses and dosing regimen have not been stable for at least 4 weeks prior to the start of Screening. If the treatment was discontinued, the discontinuation must have occurred no fewer than 2 weeks prior to the start of Screening.
 - a. This includes nutraceutical treatments and cannabinoids (tetrahydrocannabinol [THC] and cannabidiol [CBD]) which are allowable but also must meet the stability conditions above.
 - b. Pain relievers, laxatives, and anti-diarrheals may be used as needed.

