- Seizure medication: dosing regimen must have been stable 8 weeks prior to commencing IMP. Adjustments for changes in weight or age are allowable. If the treatment was discontinued, the discontinuation must have occurred no fewer than 2 weeks before the start of Screening.
- Psychotropics or any other medication used for a chronic illness (not including antibiotics, pain

Neuren Pharmaceuticals Ltd.	Clinical Trial Protocol	Version 3.0
Confidential	Neu-2591-PMS-001	October 30, 2023

relievers, anti-diarrheals, and laxatives): dosing regimen must have been stable for at least 4 weeks prior to the start of Screening. If the treatment was discontinued, the discontinuation must have occurred no fewer than 2 weeks before the start of Screening.

- This includes nutraceutical treatments and cannabinoids (THC and CBD) which are allowable but also must meet the stability conditions above.
- The Investigator should consult with the medical monitor if a subject is being treated with ocular toxic, hepatotoxic, nephrotoxic, or antibiotic medications.

The following medications/treatments are permitted and may be adjusted as needed:

- Procedural pain control medication
- Laxatives and anti-diarrheals

Standard of care immunizations and vaccinations (including COVID-19) are allowed and are not subject to the above stability conditions.

If the Investigator is unsure if a medication is permitted, the Medical Monitor should confirm if the medication is allowed and will provide written documentation to support the medication's use, if allowed. Concomitant medications will be monitored in a caregiver diary for the approximately 4 to 6 week Screening period to confirm there are no changes from the time of initial screening.

Every effort should be made to maintain stable regimens of concomitant medications and allowed nonmedicine-based therapies throughout the course of the study, with the understanding that there will be some changes to non-medicinal treatment regimens that are due to school schedules or are otherwise seasonally related.

Details of concomitant medications will be recorded in the subject notes and in the eCRF.

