• The number of concomitant medications will be summed across subjects for all unique medications that are taken while on treatment. Medications taken with a frequency of PRN or "as needed" will be excluded from the count.

5. Subject Information

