6.8. Prior and Concomitant Medications

Prior and concomitant medication verbatim terms captured via the EDC system will be mapped to Anatomical/Therapeutic/Chemical (ATC) class and Preferred Names using the September 1, 2022 version of the World Health Organization (WHO) Drug Dictionary Enhanced available.

Prior and concomitant medications will be summarized separately by WHO ATC class and preferred name. Medications with an end date prior to first dose will be considered prior medications. Medications that are taken during while on study medication will be considered concomitant medications. These summaries will present the number and percent of subjects using each medication. Subjects may have more than one medication per ATC class and preferred name. At each level of subject summarization, a subject is counted once if one or more medications at that level is reported for the subject. Each summary will be ordered by descending order of incidence of ATC class and preferred term.

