8.1.2. Secondary Efficacy Analysis

The efficacy endpoints will be analyzed using a Wilcoxon signed rank test on the paired subject data from baseline to end of treatment (Visit 16) when applicable. Descriptive statistics will be used to summarize the data. For total scores, waterfall plots, histograms, and violin plots will also be created at the End of Treatment (EOT) visit with plots for all subjects and separate plots color-coded to indicate age group (9-12 years, 6-8 years, 3-5 years), NVIQ/DQ score (≥ 50 , < 50), sex (Male, Female) and number of concomitant medications (> 6, ≤ 6). The number of concomitant medications will be determined as defined in Section 4.3. For scales with domain scores, forest plots will be generated.

Results for each efficacy variable will also be listed by subject.

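### The concomitant-medication count in SAP 4.3 is worded as a study-wide sum and, even read per child, is a post-baseline grouping factor for the efficacy plots

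*SAP*

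**What the plan says.** - SAP 4.3 (Definitions): "The number of concomitant medications will be summed across subjects for all unique medications that are taken while on treatment". The next sentence, which begins "Medications taken with a frequency of PRN or", removes as-needed drugs from the count.
- SAP 8.1.2 applies it to individual children. Total-score plots at end of treatment are colour-coded by age group, NVIQ/DQ (cut at 50), sex and "number of concomitant medications (> 6, ≤ 6). The number of concomitant medications will be determined as defined in Section 4.3".
- SAP 6.8 sets no start-date limit on what is concomitant: "Medications that are taken during while on study medication will be considered concomitant medications". Drugs that ended before first dose are classed as prior.
- Protocol 8.2 excludes children on psychotropic or other chronic-illness medication "whose doses and dosing regimen have not been stable for at least 4 weeks prior to the start of Screening". Antibiotics, pain relievers, anti-diarrheals and laxatives are exempt from that rule.
- Protocol 9.4.6 asks for stability on study: "Every effort should be made to maintain stable regimens of concomitant medications". For procedural pain control, laxatives and anti-diarrheals it says: "The following medications/treatments are permitted and may be adjusted as needed".

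Neither document defines a per-subject count or a count at baseline.

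**The concern.** There are two separate problems.

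First, the rule as written does not produce what 8.1.2 needs. The plots need one number per child, and the definition gives one number for the study. SAP section 1 makes the SAP govern over the protocol, and SAP section 4 has an independent programmer check the outputs for consistency with the plan. The rule that will be programmed should therefore be the rule that is written.

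Second, putting the wording right leaves the time window open. A scheduled antibiotic for an infection in Week 10, or a scheduled drug given for an adverse event, counts the same as a drug the child has taken for years. The other three grouping factors are not open to this: SAP 5.3 lists age and sex as demographics and NVIQ/DQ as a baseline characteristic. The count also depends on time on drug. Under Protocol 9.4.5, children who stop after Visit 5 return for the end-of-treatment assessments, so they can appear in these plots after a shorter period in which to accumulate drugs.

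At stake is how the plots are read. Protocol 6.2.3 says that one purpose of the efficacy work is to see how patient attributes at baseline relate to response. A reader who takes the >6 group as the children with heavy background medication would be reading a mixture of background therapy and on-treatment prescribing.

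**Working it through.** The plan gives no figure on this point, so there is nothing to reproduce. The check is of the text, followed by an illustration of size.

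**Step 1: the literal reading.** With 20 children (the approximate enrolment in SAP 1.2) averaging 1, 2 or 4 scheduled drugs each, a sum across subjects is 20 × 1 = 20, 20 × 2 = 40 or 20 × 4 = 80. It is a single number, and above 6 in every case, so no split of children results. The cut in 8.1.2 makes sense only for a per-child count.

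**Step 2: the per-child reading.** Which drugs enter the count?

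| Drug | Counted under 4.3? |
|---|---|
| Scheduled, started before first dose and continued | Yes |
| Scheduled, first started after first dose | Yes |
| As needed, whenever started | No |
| Ended before first dose | No (prior, under 6.8) |

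The second row makes the variable post-baseline. Since 4.3 counts every scheduled drug taken on treatment, a new start can move a child only from ≤6 to >6.

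**Step 3: where the split is used.** It is not in the covariate list in SAP 7.2 or among the covariates named in Protocol 11.4. SAP 7.3 plans no subgroup analyses, and SAP 7.5 treats all significance levels as nominal. The colour-coding in 8.1.2 is its only use.

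**Step 4: size, on assumptions.** Neither document reports how many drugs these children take. Assume that background scheduled drugs per child are Poisson with mean m, and that new scheduled drugs over 13 weeks are independent Poisson with mean l. The total is then Poisson(m + l), and the expected number of 20 children who change group is

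20 × [P(Poisson(m + l) > 6) − P(Poisson(m) > 6)].

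For example, m = 4 and l = 1 give 20 × (0.238 − 0.111) = 2.5.

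| m | >6 at first dose, of 20 | moved, l = 0.25 | l = 0.5 | l = 1 | l = 2 |
|---|---|---|---|---|---|
| 2 | 0.09 | 0.08 | 0.19 | 0.58 | 2.12 |
| 4 | 2.21 | 0.55 | 1.17 | 2.54 | 5.66 |
| 6 | 7.87 | 0.80 | 1.60 | 3.13 | 5.86 |

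For l up to 1 the range is 0.1 to 3.1 children. About 6 requires l = 2 and a background mean of 4 to 6, near the cut; for instance, m = 5 gives 20 × (0.550 − 0.238) = 6.2.

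The model adds drugs independently of response. It shows how often children would change group, not that any association with outcome would be created.

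**The case against.** The strongest reply is that this is a wording slip in a variable that only colours plots. No estimate, test or model changes. The documents never call it a baseline or background count, and Protocol 6.2.3 does not name medication among the attributes of interest. In a single-arm study there is also a case for displaying everything taken alongside the study drug, because an added drug could itself explain a change.

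The protocol also limits new starts. Chronic medication must be stable before Screening and seizure medication for 8 weeks before first dose. More than three psychotropics is exclusionary, and regimens are to be kept stable on study. Under Protocol 9.4.5, study drug is stopped for clinically significant deterioration or a need for an excluded medication, and drugs begun after that fall outside the window. Concomitant drugs are tabulated under 6.8 and CRF data are listed by subject, so a reader could trace late starts.

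Most of this stands, and it sets the limits of the point. It does not supply the missing per-subject rule. Nor does it close the window, because scheduled antibiotics, scheduled laxatives and scheduled drugs for adverse events still count. The argument for showing all drugs taken supports reporting the additions in their own right; it does not support merging them with background therapy into one unlabelled split.

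A reader might go further and infer that children who worsen drift into >6, so that heavily medicated children would falsely appear to respond less well. The documents do not support this. Worsening can lead to stopping the study drug, which shortens the window and keeps the count low, so the net direction is unknown.

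**Conclusion.** The point holds in a limited form. The definition cannot be applied literally and should be per subject. Read per subject, the split is a mixture of background and on-treatment medication, which makes it the only one of the four plot-grouping factors that can change after dosing.

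Two stronger readings should be resisted. One is that children are sorted by a consequence of treatment in place of background therapy: continuing background drugs are in the count, and an effect of treatment on it is possible but not shown. The other is that the efficacy findings are biased: no inferential result uses the split.

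The size is uncertain because it rests wholly on assumed prescribing rates: from almost none to about 3 of 20 children for up to one new scheduled drug per child, and about 6 only with two. With about 20 points on a plot, two or three recoloured children can alter its appearance. That is reason enough for a cheap correction, and no more than that.

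**What to change.** Replace the bullet in SAP 4.3 with: *For each subject, the number of background medications is the count of unique non-PRN medications started before, and ongoing at, the first dose of IMP.* Use this count for the >6/≤6 colour-coding in 8.1.2, and name it as background medication there. Report scheduled drugs started on treatment separately in the 6.8 summary and listings.

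The cost is one sentence and one date condition. SAP 4.2.1 and 6.8 already rely on medication dates, so no new data are needed. Made before database lock, the change counts as prespecified; made later, SAP section 4 requires it to be labelled post hoc.

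There are two drawbacks. Drugs added on treatment would no longer show in the plot colours, which is why they need their own summary. Also, SAP 4.2.1 imputes a start date with a missing day to the first of the month, and one with only a year to the first of January. A drug begun shortly after first dose could then be dated before it, so imputed start dates should be checked against the first-dose date before children are classified.

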5.1. Subject Disposition

Information regarding subject disposition will be summarized for all subjects by treatment group. Summaries will include the following: number of subjects enrolled, number of subjects in the ITT, Safety, and PK population, number of subjects completing the study, and number of subjects who discontinue the study early. For those who discontinue early, the primary reason for discontinuation will be summarized. A data listing by subject will also be generated.

5.2. Protocol Deviations

Protocol deviations will be collected throughout the duration of the study. Protocol deviations will be assigned a sponsor-defined category type. Each deviation will be defined as Important or non-important. In addition, a by-subject listing of all protocol deviations (important and non-important) will be produced.

5.3. Demographic and Baseline Characteristics

Demographic variables will include the following: age, sex, ethnicity, race, height at baseline, weight at baseline, and BMI at baseline. Age and BMI will be derived as specified in Section 4.3.

Baseline characteristics will include: PMS genotypes (as recorded on the CRF), history of regression, Autism Mental Status Exam, seizure clinical types at screening (as recorded on the Seizures and Spells Log and Seizure Types at Screening CRFs), presence of comorbid psychiatric disorders (e.g. Autism Spectrum Disorder (ASD), bipolar disorders, attention deficit disorder, obsessive-compulsive disorder), and Stanford-Binet Intelligence Scales version 5 (SB5) non-verbal (NVIQ) z-deviation score or the Mullen Scales of Early Learning non-verbal developmental quotient for subjects who cannot achieve basal level on the SB5 or for whom the SB-5 is developmentally inappropriate.

Demographics and baseline characteristics and will be summarized for all analysis populations (ITT Population, Safety Population, PK population).

Subjects will be evaluated for PMS at the Screening Visit. The diagnosis and genotypes will be documented. PMS genotypes will be summarized and listed by subject.

History of developmental regression will be determined from the medical history question as reported on the PMS diagnosis page in the CRF: "Has the child undergone a regression of skills in the past?" If coded as "yes" the subject is considered as having had a past developmental regression.

The Autism Mental Status Exam (AMSE) will be performed at the Screening Visit. The AMSE is an 8-item observational assessment used to document communicative and behavioral functioning in subjects with ASD. Each question is scored as 0, 1, or 2. The range of the AMSE score is 0-14. Higher scores indicate greater severity of autistic symptoms.

The scoring algorithm is below:

- 1. Question 1-4, Eye Contact, Interest in Others, Pointing Skills, Language: each response is assigned a score of 0, 1, or 2 in the order they appear on the CRF.
- 2. Question 5 Pragmatics of Language: Not Impaired or Not Applicable=0, Reported=1, Observed=2
- 3. Question 6 Repetitive Behaviors/Stereotypy: None=0, Insists on routines=1, any other response=2
- 4. Question 7-8 Unusual or Encompassing Preoccupations, Unusual Sensitivities: None=0, Reported=1, Observed=2

The AMSE score is the sum of the individual question scores above. The AMSE score and the overall impairment will be summarized.

Seizure type ("Clinical Type" in Seizures and Spells Log form on the CRF recorded at Baseline) and characteristics of seizures ("Description" in Seizure Types at Screening form on the CRF: change in awareness, loss of urine or bowel control, loss of ability to communicate, automatic repeated movements, rhythmic jerking muscle, falls if standing or sitting, head drops, warning before seizure occurred, common triggers, muscle stiffness, muscle twitch, other) are recorded at the Screening Visit for subjects. These descriptive characteristics will be summarized using frequencies and percentages.

The presence of other co-morbid psychiatric disorders will be recorded on the PMS diagnosis page of the CRF. If the disorder is checked on the CRF, it will be considered as present in the subject.

5.4. Medical History

Medical history will be coded using MedDRA version 25.1 and listed by System Organ Class (SOC), Preferred Term (PT), and verbatim term. A complete medical history will

be recorded at all Screening and Baseline visits (Visits 1, 2, 3). Medical history will be summarized using frequencies and percentages according to the SOC and PT.

6. Safety Analysis

The primary objective of the study is to investigate the safety, tolerability, and pharmacokinetics of treatment with NNZ-2591 in children and adolescents with PMS.

All safety analyses will be based on the Safety Population.

Safety will be assessed based on incidence of treatment emergent adverse events (TEAEs), serious adverse events (SAEs), changes in vital signs, changes in laboratory measures, neurological, ophthalmological, and physical exam results, renal ultrasound findings, and changes in ECG's. In addition to the outputs (tables, listings, shift tables) described below for each safety variable, other visual presentations of the data may be generated (e.g., volcano plots) as appropriate.

Tolerability will be assessed based on daily dosing logs, required dosing adjustments or discontinuations, dosing compliance, and AEs related to reported subject experience.

Pharmacokinetics will be summarized separately outside of this SAP.

6.1. Dosing Summary

Treatment duration and study duration will be derived as stated in Section 4.3 and summarized using descriptive statistics.

The maximum dose (4 mg/kg BID, 8 mg/kg BID, or 12 mg/kg BID) of each subject will be summarized according to the Dosing Compliance CRF as a frequency distribution. The number of missed doses, as recorded in the Daily Dosing Log CRF, will be summarized.

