¹ The daily dosing log in the Caregiver Diary will be reviewed at all post-baseline visits through EOT. If any doses are missed or mis-dosed, this should be queried with the caregiver and appropriate feedback given to the family. This feedback should be documented in the source documents. At the in-home nurse visit, the nurse will review the caregiver diary to check any issues and provide feedback to the family at the visit. The nurse will notify the site about any urgent issues the day of the visit and note anything else in the source documents. The nurse does not sign the daily dosing log/summary page. The source documents and the diary will be sent to the site. The Investigator (or appropriately credentialed delegee) will review the diary and source documents collected at the in-home visit.

^m Coagulation includes prothrombin time, activated partial thromboplastin (aPTT), and international normalized ratio (INR).

ⁿ A Comprehensive Metabolic Panel will be assessed every post-enrollment visit (see Section 9.5.2). If abnormal findings are observed on renal or liver function tests, additional tests as is clinically indicated may be conducted as described in Sections 9.5.2.1 and 9.5.2.3).

^oBoth urinalysis and a urine screen for drugs of abuse will be evaluated at Screening (See Section 9.5.2).

^p For female subjects who have reached menarche.

^q See Table 2 and Table 3 for PK blood collection times.

^r The Mullen is done for subjects who cannot obtain basal on SB5 or for whom the SB5 is developmentally inappropriate.

^s The study exit form should also be completed if the subject terminates the study early.

Table 2 Pharmacokinetic Blood Sampling Schedule (Subjects Ages 7 to 12 Years Old)

Week	Visit No.	Treatment	Timing of Sample (relative to start of dosing) ^a	Sample Time Point
2	5		Pre dose (-120 to -15 minutes) ^b	1
			1-3 hours post dose ^c	2
			4-7 hours post dose ^c	3
6	9	Mid-treatment	Pre dose (-120 to -15 minutes) ^b	4
			1-3 hours post dose ^c	5
			4-7 hours post dose ^c	6
13	16	End of Treatment	Pre dose (-120 to -15 minutes) ^b	7
			1-3 hours post dose ^c	8
			4-7 hours post dose ^c	9

^a All post-dose windows are determined from the first dose of the visit (morning dose) and all PK samples must be collected before the second dose (PM dose).

^b Pre dose counts as both T0 and 12 hours post dose from previous evening (near trough). The previous evening's dose should be taken in the evening as late as possible, preferably before bedtime.

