9.4.3 Treatment Compliance

The timing of administration of the IMP should be at approximately the same time each day. Each day there will be two dose administrations, one in morning and one in afternoon or evening. There should be at least 8 hours between doses. Doses should be taken by mouth either from a cup or via a dosing syringe provided by the pharmacist. Doses should be given on an empty stomach (2 hours after the previous meal or snack and 30 minutes prior to the next). The IMP should not be mixed with water, liquid thickeners, or food for administration. Doses may be taken over a 10-minute period with a follow up of 250 mL of water.

The treatment times will be recorded in the Caregiver Diary and then entered into the eCRF. A Study Monitor will review subject source documents and IMP accountability records to assess treatment compliance on an ongoing basis during site visits. Subjects who receive $\geq 80\%$ and $\leq 120\%$ of IMP, administered in accordance with the protocol are considered compliant.

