12.3 Overdose

Subjects should not exceed the maximum daily doses or take any two doses within an 8-hour interval. If an administered dose is spat out, regurgitated, or vomited, the dose should NOT be re-administered, and this should be documented in the dosing diary or the source documents for the in-clinic dose. There is no specific antidote to NNZ-2591 IMP. In the event of an overdose, appropriate supportive measures should be employed as clinically indicated and the Medical Monitor must be informed immediately.

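### SAP 6.1 reports adherence only as a raw count of missed doses, so no planned analysis applies the protocol's 80–120% compliance definition, and lost doses have no counting rule

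*SAP*

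**What the plan says.** Protocol 6.3.1.1 lists dosing compliance among the elements of the primary tolerability endpoint. SAP Section 6 (Safety Analysis) repeats it: "Tolerability will be assessed based on daily dosing logs, required dosing adjustments or discontinuations, dosing compliance, and AEs related to reported subject experience".

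Protocol 9.4.3 defines compliance as a share. Children who receive at least 80% and at most 120% "of IMP, administered in accordance with the protocol are considered compliant".

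SAP 6.1 (Dosing Summary) plans four items: treatment duration, study duration, maximum dose level and missed doses. The maximum dose "of each subject will be summarized according to the Dosing Compliance CRF as a frequency distribution"; this is the SAP's only stated use of that form. For adherence, it says: "The number of missed doses, as recorded in the Daily Dosing Log CRF, will be summarized".

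SAP 4.3 (Definitions) derives BMI, seizure rates and a concomitant-medication count, but no compliance percentage. The 80% and 120% limits do not appear in the SAP. SAP Section 1 makes the SAP govern where the two documents differ on planned analyses.

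On doses that are given but not fully delivered, Protocol 12.3 says: "If an administered dose is spat out, regurgitated, or vomited, the dose should NOT be re-administered". It requires the event to be documented in the dosing diary, or in source documents for the in-clinic dose. Protocol Table 1, footnote l, says: "If any doses are missed or mis-dosed, this should be queried with the caregiver". Neither document defines a missed dose.

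**The concern.** The protocol gives a component of the primary tolerability endpoint a numerical definition, but no planned analysis applies it. The quantity planned instead differs from it in three ways.

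- **No denominator.** Children with shorter exposure have fewer doses to miss, so the count falls when a child stops early.
- **One direction only.** A count of missed doses carries no information about the 120% limit.
- **An undefined term.** Protocol 12.3 describes a spat-out or vomited dose as administered, and footnote l names mis-dosed separately from missed. On that wording such doses may not be counted as missed, and sites could differ in how they code them.

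The last point matters in this population. Protocol 5.1 reports cyclic vomiting in up to 25% of individuals with the syndrome and describes feeding problems, choking and gagging as common. The product is an oral liquid taken twice daily. At stake is whether the dosing table tells a reader how much of the assigned drug the children received.

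**Working it through.** Neither document states a compliance result, so there is no plan figure to reproduce. The check is on how the planned count behaves against the protocol's percentage.

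**Inputs**
- Dosing is twice daily for at most 91 days (Protocol 9.4.2; 13 weeks × 7 = 91).
- Day 1 may hold one or two doses (Protocol 9.4.2), so a full course is 181 or 182 doses. 182 is used below.
- The titration schedule is three weeks at 4, three at 8 and seven at 12 mg/kg BID (Protocol synopsis and Table 4). The dose is fixed on Baseline weight (Protocol 7.2.1), so shares of mg/kg equal shares of mg.

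**1. Where the 80% line falls.** 0.80 × 182 = 145.6, so 146 doses are needed and 36 may be missed. For a child treated for 14 days (28 doses), 0.80 × 28 = 22.4, so 23 are needed and 5 may be missed.

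**2. The same count can mean different adherence.** Percent = (assigned − missed) / assigned.
- 6 missed over 91 days: 176/182 = 96.7%.
- 6 missed over 14 days: 22/28 = 78.6%, below the criterion.

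**3. The ranking can reverse.**
- Stops on Day 20, 4 missed: 4/40 = 10.0% missed. Completer, 10 missed: 10/182 = 5.5% missed. The count ranks the first child as better.
- Stops at 21 days, 9 missed: 33/42 = 78.6%, fails. Completer, 20 missed: 162/182 = 89.0%, passes. Again the count favours the early stopper.
- At an equal 10% miss rate, the expected counts are 4.2 at 21 days, 8.4 at 42 days and 18.2 at 91 days.

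**4. Doses and amount differ.** Planned total = 42 × 4 + 42 × 8 + 98 × 12 = 1680 mg/kg. Missing 36 doses is 146/182 = 80.2% by count. By amount it is:

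| All 36 missed at | Amount received |
|---|---|
| 4 mg/kg | 1 − 144/1680 = 91.4% |
| 8 mg/kg | 1 − 288/1680 = 82.9% |
| 12 mg/kg | 1 − 432/1680 = 74.3% |

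**5. Lost doses, under an assumption.** Suppose spat-out or vomited doses are not coded as missed; the documents do not say. In a full course with no other loss:

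| Doses lost | Retained | Missed doses shown |
|---|---|---|
| 10 | 172/182 = 94.5% | 0 |
| 20 | 162/182 = 89.0% | 0 |
| 37 | 145/182 = 79.7% | 0 |

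If they are coded as missed, this discrepancy disappears; steps 1 to 4 are unaffected.

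**The case against.** The best reply is that this is a gap in presentation with little consequence. Treatment duration is summarized in the same section. Discontinuations and their reasons are tabulated and listed (SAP 5.1), and all CRF data are listed by subject (SAP Section 9). With about 20 children, a reader could relate missed doses to days on drug. A monitor reviews compliance from source and accountability records (Protocol 9.4.3). Vomiting that qualifies as an adverse event appears in the TEAE tables (SAP 6.2). No analysis set uses the 80% threshold: efficacy is ITT, safety covers all dosed children, and the SAP has no per-protocol set.

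Much of this stands, and it rules out three stronger readings that a reader might infer.

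- **That the count scores vomited, spat-out and mis-measured doses as taken.** The documents contain no such rule. Missed is undefined and the coding of the dosing log is not shown. This is a missing definition.
- **That compliance is never evaluated.** Monitor review and the listings mean it can be looked at. What is missing is a planned derivation and table.
- **That neither safety nor efficacy can be read against drug received.** Blood concentrations at Weeks 2, 6 and 13 (Protocol 11.5), maximum dose and treatment duration all bear on exposure.

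The reply does not remove the main point. Monitoring is site oversight with no specified result. Group-level treatment duration does not give any child's rate. Working from listings leaves the numerator, the denominator and the handling of lost doses to be chosen after the data are seen, and with about 20 children, reclassifying one moves the compliant proportion by 1/20 = 5 percentage points.

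**Conclusion.** The concern holds as a gap between the protocol's definition and the SAP's output. SAP 6.1 plans a missed-dose count without a denominator. No planned analysis applies the 80–120% criterion, although dosing compliance belongs to the primary tolerability endpoint. That the count can misorder children with unequal exposure, and cannot show the upper limit, follows from arithmetic alone.

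The treatment of spat-out, vomited and mis-dosed administrations is an open question in the documents. The 37-dose illustration (79.7% retained, zero missed) holds only if such doses are not coded as missed. Nor do the documents support scoring every vomited dose as zero: they give no interval between dose and vomiting, and some of the drug may have been absorbed.

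The effect is limited to a descriptive component of tolerability. The change is worth making because it is cheap and supplies the quantity the protocol defines.

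**What to change.** Keep the missed-dose count and add the following.

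1. In SAP 4.3, define percent compliance as doses received divided by doses assigned from first to last dose, at the dose level then assigned. Define the same quantity in mg where administered amounts are recorded. The 120% limit can be checked only where amounts or extra doses are recorded.
2. In SAP 4.3, define a missed dose, and say how spat-out, regurgitated, vomited and mis-dosed administrations are classified.
3. In SAP 6.1, report percent compliance overall and by dose level, with the number of children within 80–120%.
4. Show spat-out, regurgitated or vomited doses and mis-dosed administrations in their own row. Give percent compliance twice, counting them as received and as not received, so that no absorption assumption is needed.

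The cost is SAP wording and one extra derived variable, and reported compliance may look slightly less favourable. One point to confirm first is what reaches the database. Protocol 9.4.3 says treatment times are entered in the eCRF, and footnote l puts feedback on mis-doses in source documents. Amounts for mis-doses may therefore not be in the database, in which case the mg version is limited accordingly. No dosing or clinical rule is affected.
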